The toxicity potential of MK-3682 has been well characterized in *in vitro* mitochondrial toxicity assays, a battery of *in vitro* and *in vivo* genetic toxicity studies, safety pharmacology studies, and 4-week, 3-month and 6-month repeat-dose oral toxicity studies in rats and monkeys. *In vitro* and *in vivo* preclinical data demonstrate that MK-3682 and its metabolite, M6, at the exposures observed in the clinic, have limited potential for class toxicities associated with nucleotides, including myopathy and mitochondrial toxicity. No observed adverse effect levels (NOAELs) in the rat and Cynomolgus monkey at 1000 mg/kg/day provide adequate margins of safety relative to anticipated human doses and support daily oral dosing of humans for up to 6 months in duration. In summary, the toxicity studies identified minimal differences between control and treated animals, all of which were not considered adverse. Preclinical studies identified the liver and potentially kidney as potential target organs. There was no evidence of cardiovascular toxicity in studies up to 3 months' duration, based on histopathology in the rat and monkey and echocardiography, electrocardiography, and serum biomarker evaluations in the monkey. Overall, the preclinical toxicity profile of MK-3682 via the oral route of administration supports the continuation of clinical trials.

To date, MK-3682 has been generally well-tolerated in healthy subjects and HCV-infected subjects in several Phase 1 clinical studies at single doses up to 900 mg, multiple doses up to

750 mg per day for 10 days, and in Phase 2a trials of 300 mg or 450 mg once daily for up to 24 weeks. Review of the safety data has revealed no clinically significant abnormalities in routine physical examinations including vital signs. There have been no dose-related or other patterns observed in the clinical, ECG, or laboratory data. In the clinical studies proposed, available safety data (clinical and laboratory AEs, vital signs, laboratory safety tests, and ECGs) will be carefully monitored.

Phase 2 studies have demonstrated that a regimen of MK-3682 (450 mg)/GZR/RZR is highly effective in GT1, 2, and 3-infected subjects. Overall, MK-3682, as a component of a combination DAA regimen, has the potential to substantially improve HCV treatment outcomes, benefiting many HCV-infected individuals.

RZR

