7.1.5.3 Treatment Period

Treatment Day 1 (Visit 2)

Subjects should fast overnight prior to reporting to the study site for dosing on Treatment Day 1 (Visit 2).

Pre- and Post-Treatment Procedures

Day 1 procedures listed on the Trial Flow Chart should be performed prior to dosing unless specified otherwise. For female subjects of reproductive potential, a urine pregnancy test will be performed at the site prior to study drug initiation. If the urine pregnancy test result is negative, the subject will be eligible for allocation and the remainder of the pretreatment (Day 1) testing/procedures will be performed. If the urine pregnancy test result is positive, a serum pregnancy test will be performed. If the result of the serum pregnancy test is positive, the subject must not be randomized or allocated to treatment in the study.

Blood and urine will be collected for assay of safety evaluations, including plasma HCV RNA, plasma HIV RNA (only for HIV co-infected subjects), and PK measurements. These samples will be sent to the appropriate central laboratory(ies) following the procedure(s) set forth in the manual(s).

Additional samples will be collected for genetic evaluation of host parameters related to the response of HCV subjects to MK-3682 and RZR.

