7.2.3.2 Events of Clinical Interest

Selected non-serious and serious adverse events are also known as Events of Clinical Interest (ECI) and must be reported to the Sponsor.

For the time period beginning when the consent form is signed until treatment allocation/randomization, any ECI, or follow up to an ECI, that occurs to any subject must be reported within 24 hours to the Sponsor if it causes the subject to be excluded from the trial, or is the result of a protocol-specified intervention, including but not limited to washout or discontinuation of usual therapy, diet, placebo treatment or a procedure.

For the time period beginning at treatment allocation/randomization through 14 days following cessation of treatment, any ECI, or follow up to an ECI, whether or not related to the Sponsor's product, must be reported within 24 hours to the Sponsor, either by electronic media or paper. Electronic reporting procedures can be found in the EDC data entry guidelines. Paper reporting procedures can be found in the Investigator Trial File Binder (or equivalent).

Events of clinical interest for this trial include:

1. an overdose of Sponsor's product, as defined in Section 7.2.1 - Definition of an Overdose for This Protocol and Reporting of Overdose to the Sponsor, that is not associated with clinical symptoms or abnormal laboratory results.
2. first instance of ALT or AST >500 IU/L from the initiation of study therapy through 14 days following treatment.*
3. first instance of ALT or AST >3x nadir AND >3X ULN from the initiation of study therapy through 14 days following treatment.*

*Note: The purpose of the criteria is to specify a threshold of abnormal hepatic tests that may require and additional evaluation for an underlying etiology. The trial site guidance for assessment and the follow up of these criteria can be found in the Investigator Trial File Binders (or equivalent)

4. first instance of eGFR <50 mL/min/1.73 m² from the initiation of study therapy through 14 days following treatment. Creatinine clearance will be evaluated as an estimated GFR (eGFR), based on the modification of diet in renal disease (MDRD) equation:

$$\text{eGFR (mL/min/1.73 m}^2\text{)} = 175 \times (\text{Scr, std})^{-1.154} \times (\text{Age})^{-0.203} \times (0.742 \text{ if female}) \times (1.212 \text{ if black})$$

Scr, std: serum creatinine measured with a standardized assay

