
Statistical Methods for Key Safety Analyses
	
The ASaT population will be used for safety analyses. The proportion of subjects with AEs of elevated laboratory values that are reported as ECIs (as described in Section 7.2.3.2) during the study therapy period will be provided along with the corresponding 95% CIs.
 
In addition, the broad clinical and laboratory AE categories consisting of the percentage of subjects with any AE, a drug-related AE, an SAE, an AE which is both drug-related and serious, and who discontinued due to an AE will be summarized in the same manner.

Interim Analyses
	
An assessment of safety for the first 50 subjects will be made. (See Section 5.11.1 for the criteria for assessing safety in the first 50 subjects.) In addition, an assessment for efficacy will be made for the first 10 per-protocol subjects enrolled in each GT, and on an ongoing basis to determine whether there is a need to modify the treatment regimen. (See Section 5.11.4 for the criteria for assessing efficacy and the initiation of treatment modifications). Finally, throughout the course of this open-label study, efficacy and safety will be monitored for trends and programmatic decisions.

Multiplicity
	
No multiplicity adjustment is planned for the study.

Sample Size and Power
	
Approximately 250 subjects will be allocated to treatment, with 35 GT1a-, 15 GT1b-, 50 GT2-, 50 GT3-, 50 GT4-, 25 GT5- and 25 GT6-infected subjects.
 
If the SVR₁₂ rate is approximately 97.1% for GT1a (34 successes out of 35), the exact 95% CI is (85.1, 99.9). If the SVR₁₂ rate is approximately 93.3% for GT1b (14 successes out of 15), the exact 95% CI is (68.1, 99.8).
 
For GT2, GT3, and GT4 where 50 subjects are targeted for treatment allocation, if the SVR₁₂ rate is 98% (49 successes out of 50), the exact 95% CI is (89.4, 99.9). If the SVR₁₂ rate is 94% (47 successes out of 50), the exact 95% CI is (83.5, 98.7).
 
For GT5 and GT6 where 25 subjects are targeted for treatment allocation, if the SVR₁₂ rate is 96% (24 successes out of 25), the exact 95% CI is (79.6, 99.9). If the SVR₁₂ rate is 92% (23 successes out of 25), the exact 95% CI is (74.0, 99.0).
 
Detailed information for varying SVR rates is in Section 8.9.1.

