8.6.2 Statistical Methods for Safety Analyses

Safety and tolerability will be assessed by clinical review of all relevant parameters including AEs and laboratory parameters. The 95% CIs for the safety parameters will be estimated

using the Clopper-Pearson method [42], which is a conservative exact method of providing CIs in this estimation study.

The analysis of safety parameters will follow a tiered approach (Table 17). The tiers differ with respect to the analyses that will be performed.

The first tier includes (1) AEs of elevated laboratory values that are reported as ECIs described in Section 7.2.3.2; (2) at least 1 AE; (3) a drug-related AE; (4) an SAE; (5) a serious and drug-related AE, and (6) an AE leading to discontinuation. Point estimates and 95% CIs will be provided.

The second tier includes specific AEs by SOC, vital signs, 12-lead ECGs, and standard laboratory safety tests at time points specified in the Trial Flow Chart (Section 6.0). Point estimates will be provided.

Missing safety laboratory, vital signs, or ECG values will be handled using the Data-As-Observed approach, that is, any missing value will be excluded from the analysis. The only exception is when a Baseline/Day 1 result is missing, this will be replaced with the latest pre-treatment result, if available.

Missing safety laboratory, vital signs, or ECG values will be handled using the Data-As-Observed approach, that is, any missing value will be excluded from the analysis. The only exception is when a Baseline/Day 1 result is missing, this will be replaced with the latest pre-treatment result, if available.

The primary safety analysis will summarize the safety data for subjects during the treatment period plus 14 days of follow-up.

Table 17 Analysis Strategy for Safety Parameters

Safety Endpoint ¹	95% CI	Descriptive Statistics
AEs of elevated laboratory values that are reported as ECIs	X	X
Any AE	X	X
Any SAE	X	X
Any Drug-Related AE	X	X
Any Serious and Drug-Related AE	X	X
Discontinuation due to AE	X	X
Specific AEs, SOCs or PDLCS		X
Change from Baseline Results (laboratory, vital signs, ECG)		X

AE = adverse event; ECG = electrocardiogram; ECI = event of clinical importance; n/a = not applicable; PDLC = pre-defined limit of change; SOC = system organ class; X = results will be provided.

¹ Adverse Experience references refer to both Clinical and Laboratory AEs.

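### The first-tier laboratory safety rate counts site-reported ECIs of 'elevated' values in what reads as one proportion; it is better derived, criterion by criterion, from the measured values

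*Combined protocol and SAP*

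**What the plan says.** Section 8.6.2 sorts safety parameters into two tiers. The first tier gets point estimates and 95% confidence intervals. Its only specifically laboratory item is "AEs of elevated laboratory values that are reported as ECIs described in Section 7.2.3.2". Section 8.1 states the same endpoint in the singular, "The proportion of subjects with AEs of elevated laboratory values that are reported as ECIs", and confines it to the period of study therapy. Table 17 shows it as one row.

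The second tier covers the measured values: "standard laboratory safety tests at time points specified in the Trial Flow Chart (Section 6.0). Point estimates will be provided". In Table 17 the row "Specific AEs, SOCs or PDLCS" and the change-from-baseline row get descriptive statistics without an interval. PDLC is spelled out only in the table's abbreviation note. No limits are given, and Section 8.6.3 does not name PDLCs among the items deferred to the supplemental SAP.

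Section 7.2.3.2 lists four laboratory criteria:

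- "first instance of ALT or AST >500 IU/L from the initiation of study therapy through 14 days following treatment"
- "first instance of ALT or AST >3x nadir AND >3X ULN from the initiation of study therapy through 14 days following treatment"
- a first eGFR below 50 mL/min/1.73 m²
- a first creatinine of Grade 2 or higher (above 1.3 × ULN) that is also above baseline

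Each must be reported to the sponsor within 24 hours, whether or not it is judged related to treatment. Section 4.3 says of MK-3682: "Preclinical studies identified the liver and potentially kidney as potential target organs".

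**The concern.** Safety is a primary objective (Section 3.1), and the liver and potentially the kidney are the organs to watch. The endpoint meant to carry the laboratory part of that objective with an interval depends on a chain of steps. The site must notice the crossing, which for one liver criterion means tracking a running nadir. It must file the event. The event must then still count as an elevated laboratory value, even if a diagnosis is recorded as its cause. A break at any step lowers the rate, although the numbers that define the event have been measured.

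The wording also leaves three things open: whether liver and kidney criteria get separate rates, whether a low eGFR belongs under 'elevated', and whether the 14 days after treatment count. Two programmers could produce different tables from the same text.

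**Working it through.** **1. Can each criterion be computed from planned data?** Table 12 lists ALT, AST, creatinine and eGFR under chemistry. The flow chart schedules chemistry at Day 1, Day 7 and TW2, 4, 6, 8, 10 and 12 (also TW14 and TW16 if treatment is extended).

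| Criterion (7.2.3.2) | Organ | Direction | Needs |
|---|---|---|---|
| ALT/AST >500 IU/L | liver | high | value |
| ALT/AST >3x nadir and >3x ULN | liver | high | running minimum, ULN |
| eGFR <50 | kidney | **low** | value |
| creatinine >1.3x ULN and above baseline | kidney | high | ULN, baseline |

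All four can be computed. Section 8.5.2 already supplies the inclusion rule (at least one post-dose value, plus a baseline where change is assessed). The third criterion does not fit the word 'elevated'.

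**2. Window.** Section 8.1 uses the study therapy period. Section 8.6.2 and the 7.2.3.2 definitions use treatment plus 14 days. The flow chart has no nominal visit between the last treatment visit and FW4, so the events at stake would come mainly from early-discontinuation and unscheduled visits. The number is probably small, but the two definitions differ.

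**3. Reproduce the plan's own figures.** For x events in n = 250, the two-sided 95% Clopper-Pearson limits are: lower = Beta⁻¹(0.025; x, n−x+1), upper = Beta⁻¹(0.975; x+1, n−x). The upper limits for x = 0, 1, 5, 10, 20, 30, 40, 50 are 1.46, 2.21, 4.61, 7.23, 12.09, 16.69, 21.14 and 25.50%. Rounded, these match all eight rows of Table 19. No stated figure is wrong.

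**4. Effect of incomplete reporting.** The documents give no reporting completeness, so it is assumed to lie between 50% and 100%. Also assume that 10 of 250 subjects truly cross a threshold and that every report reflects a real crossing. Reported count = 10 × completeness.

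| Completeness | Reported | Rate (95% CI) |
|---|---|---|
| 100% | 10/250 | 4.0% (1.9–7.2) |
| 90% | 9/250 | 3.6% (1.7–6.7) |
| 70% | 7/250 | 2.8% (1.1–5.7) |
| 50% | 5/250 | 2.0% (0.7–4.6) |

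Under these assumptions the reported rate equals the measured rate or falls below it; it cannot exceed it.

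**5. Effect of one combined row.** Assume that no subject meets both a liver and a kidney criterion. A combined 10/250 = 4.0% (1.9–7.2) is the same line in each of these cases:

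| Liver / kidney | Liver 95% CI | Kidney 95% CI |
|---|---|---|
| 10 / 0 | 1.9–7.2% | 0–1.5% |
| 5 / 5 | 0.7–4.6% | 0.7–4.6% |
| 0 / 10 | 0–1.5% | 1.9–7.2% |

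**The case against.** The strongest defence is that crossing a listed threshold is itself the ECI. The triggers are objective, reporting is mandatory within 24 hours regardless of relatedness, and site guidance on the hepatic criteria sits in the trial file binder. Tracking a nadir is no extra burden, because Table 11 already requires it. Section 7.1.5.7 brings subjects with a laboratory ECI at the last dosing visit back weekly. All of this stands. A reader might infer that crossings *are* under-counted; the documents support only a possibility, of unknown size.

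The defence also limits four other tempting readings:

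- *Liver and kidney are pooled.* This is the natural reading of one row and a singular proportion, but it is not stated. Section 8.1 has plural intervals and Section 8.6.2 plural AEs and point estimates, so display by criterion remains possible.
- *A liver signal could not be told from a renal one.* Not for the plan as a whole: the second tier shows ALT, AST and creatinine as separate analytes and AEs by SOC.
- *This is the only rate with an interval that covers laboratory events.* The note to Table 17 says AE references include laboratory AEs, so the any-AE, drug-related, serious and discontinuation rates cover them too.
- *Every value is held centrally.* Section 7.1.5.3 states shipment to a central laboratory under Day 1 procedures. Central handling of later visits and repeat tests is plausible but not stated there.

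Finally, this is a single-arm estimation study, and no stopping rule uses the first-tier rate; Sections 5.11.1 and 5.11.2 list their liver and kidney criteria separately. That lowers the stakes but does not make a count of reports preferable to a count of measured crossings.

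**Conclusion.** The point holds as a minor, low-cost improvement. The first-tier laboratory line is defined by reports rather than measurements. It is not stated to be split by organ or criterion, taken literally it omits one of the two kidney criteria, and it carries two different windows. The second tier does not close the gap: it has no intervals, states no PDLC limits and specifies no count of ECI-threshold crossings from measured values.

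No bias has been shown. The illustrated fall from 4.0% to 3.6% or 2.8% rests on an assumed 10 true crossers and assumed completeness of 90% and 70%. The intervals overlap heavily, and with complete reporting the difference is zero. The firmer part of the finding is the wording: the excluded low eGFR, the unstated separation and the conflicting windows can be seen on the page without any assumption.

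**What to change.** In Sections 8.1 and 8.6.2 and in Table 17:

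- Derive each of the four 7.2.3.2 laboratory criteria from the laboratory dataset, in ASaT subjects with at least one post-dose value, over treatment plus 14 days.
- Give one row per criterion with n/N and the Clopper-Pearson 95% CI. Note that a subject can appear in more than one row, so the rows do not add up.
- Replace 'elevated' with 'abnormal', so that a low eGFR is included.
- Align the window in Section 8.1 with that in Section 8.6.2.
- State the PDLC limits, or say that the 7.2.3.2 thresholds serve as those limits.
- List site-reported ECIs separately and reconcile them with the derived counts. This also catches any reported value that is not in the laboratory dataset.

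The cost is SAP wording and minor programming. No new data are needed, and sample size and patient management are unchanged. The one downside for the sponsor is that the stated rate may come out slightly higher.

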8.6.3 Summaries of Baseline Characteristics, Demographics, and other Analyses

Summaries of demographic and baseline characteristics, PK analyses, and analyses for the exploratory endpoints will be described in detail in the supplementary statistical analysis plan (sSAP).

8.7 Interim Analyses

An assessment of safety for the first 50 subjects will be made when the last of these subjects reaches TW4. The criteria for assessing safety in this cohort of 50 subjects can be found in

Section 5.11.1. Specifically, if >3 out of the first 50 subjects receiving MK-3682 + RZR experience any of the listed criteria, study therapy will be discontinued in all subjects and no additional subjects will be allocated to treatment.

In addition to the safety assessment for the first 50 subjects, criteria for early stopping at any point in the trial is given in Section 5.11.2 and for pausing treatment allocation is given in Section 5.11.3.

An assessment of efficacy will be made when the first 10 per-protocol subjects within each GT (GT1-6) have reached FW4. If ≥ 3 out of the first 10 subjects in the PP population for each GT (GT1-6) receiving 12 weeks of therapy experience virologic failure (non-response, rebound, breakthrough, or relapse) by FW4, no additional subjects for that particular GT will be allocated to treatment in the trial. Additionally, if the majority of failures are due to relapses (i.e., $>50\%$), the treatment regimen with MK-3682 + RZR for subjects with a particular GT will be extended to 16 weeks' duration and RBV will be added for subjects with this GT who remain on treatment.

In addition, efficacy will continue to be monitored throughout the trial and if >5 of subjects in the PP population for GT1-4, and >3 subjects in the PP population for GT5-6, experience virologic failure at any point in the trial, no additional subjects for that particular GT will be allocated to treatment. Additionally, if the majority of failures are due to relapses (i.e., $>50\%$), the treatment regimen with MK-3682 + RZR for subjects with a particular GT will be extended to 16 weeks' duration and RBV will be added for subjects with this GT who remain on treatment.

Finally, throughout the course of this open-label study, efficacy and safety will be monitored for trends and programmatic decisions.

8.8 Multiplicity

No multiplicity adjustment is planned for the study.

8.9 Sample Size and Power Calculations

8.9.1 Efficacy Analysis

Approximately 250 subjects will be allocated to treatment with a target allocation of 35 GT1a-, 15 GT1b-, 50 GT2-, 50 GT3-, 50 GT4-, 25 GT5-, and 25 GT6-infected subjects. These sample sizes were chosen to provide sufficient confidence of the estimated treatment response rate for the most prevalent GTs (Section 4.2.3)

Table 18 below shows the 2-sided 95% CIs for SVR_{12} under varying assumptions of the number of successes in the FAS population for each GT. Note that these intervals are not symmetric around the point estimate.

Table 18 Two-Sided 95% Confidence Intervals for SVR12 (FAS Population)

Number of subjects in FAS population	Observed Number of Successes (%)	Two-Sided 95% Confidence Interval ¹
15	15 (100.0%)	(78.2, 100.0)
	14 (93.3%)	(68.1, 99.8)
	13 (86.7%)	(59.5, 98.3)
	12 (80.0%)	(51.9, 95.7)
25	25 (100.0%)	(86.3, 100.0)
	24 (96.0%)	(79.6, 99.9)
	23 (92.0%)	(74.0, 99.0)
	22 (88.0%)	(68.8, 97.5)
35	35 (100.0%)	(90.0, 100.0)
	34 (97.1%)	(85.1, 99.9)
	33 (94.3%)	(80.8, 99.3)
	32 (91.4%)	(76.9, 98.2)
50	50 (100.0%)	(92.9, 100.0)
	49 (98.0%)	(89.4, 99.9)
	48 (96.0%)	(86.3, 99.5)
	47 (94.0%)	(83.5, 98.7)
FAS = Full Analysis Set.		
¹ Based on the Clopper-Pearson method		

8.9.2 Safety Analysis

The primary safety objective of this study will be addressed by a review of the accumulated safety data. Certain safety endpoints of special interest have been identified in Section 8.4.2.

The ASaT population will include approximately 250 subjects. The upper bound of the 95% CI for the underlying percentage of subjects with a specific AE given various hypothetical observed number of subjects with that specific AE within the study are provided in [Table 19](#). These calculations are based on the exact binomial method proposed by Clopper and Pearson [42].

Table 19 Estimate of Incidence of a Specific AE and 95% Upper Confidence Bound Based on a Hypothetical Number of Subjects with that Specific AE

n	Hypothetical Number of Subjects with AE	Estimate of Incidence	95% Upper Confidence Bound ¹
250	0	0.0%	1.5%
	1	0.4%	2.2%
	5	2.0%	4.6%
	10	4.0%	7.2%
	20	8.0%	12.1%
	30	12.0%	16.7%
	40	16.0%	21.1%
	50	20.0%	25.5%

AE = adverse event.
¹ Based on the 2-tailed exact confidence interval of a binomial proportion (Clopper and Pearson, 1934)

